### 3.1.7. Dose-limiting Toxicities

A DLT is defined as any TEAE not attributable to disease or disease-related processes that occurs during the DLT evaluation period (Day 1 to Day 21 in Cycle 1 of Dose Escalation Part) and is Grade 3 or above according to National Cancer Institute Common Terminology Criteria for Adverse Events (NCI-CTCAE) version 5.0, with the exceptions as defined below:

For hematological toxicities, a DLT is defined as follows:

- Grade 4 neutrophil count decreased lasting >7 days, neutrophil count decreased that requires standard therapies, such as colony stimulating factor (CSF)
- Grade ≥3 febrile neutropenia
- Grade 4 anemia
- Grade 4 platelet count decreased

- Grade  $\geq$ 3 platelet count decreased lasting >7 days
- Grade ≥3 platelet count decreased with clinically significant hemorrhage
- Grade 4 lymphocyte count decreased lasting ≥14 days

For hepatic organ toxicities, a DLT is defined as follows:

- Serum aspartate aminotransferase (AST) or serum alanine aminotransferase (ALT) >20  $\times$  upper limit of normal (ULN)
- AST or ALT >5 × ULN, if accompanied by blood bilirubin >1.5 × ULN
- In subjects without liver metastases, AST or ALT  $>5 \times$  ULN lasting >3 days
- In subjects with liver metastases, AST or ALT >5 × ULN lasting >3 days, if the baseline level was <3 × ULN
- In subjects with liver metastases, AST or ALT  $> 8 \times ULN$  lasting > 3 days, if the baseline level was  $> 3 \times ULN$

For non-hematological, non-hepatic major organ toxicities, a DLT is defined as follows:

- Symptomatic congestive heart failure (CHF)
- Left ventricular ejection fraction (LVEF) decline to <40% or >20% drop from baseline
- Other Grade ≥3 non-hematological, non-hepatic major organ toxicities

The following TEAEs are NOT considered DLTs:

- Grade 3 fatigue lasting <7 days
- Grade 3 nausea, vomiting, diarrhea, or anorexia that has resolved to Grade ≤2 within 3 days
- Isolated laboratory findings not associated with signs or symptoms including Grade 3/4 serum alkaline phosphatase (ALP) increased, hyperuricemia, serum amylase increased, and lipase increased, and Grade 3 hyponatremia lasting <72 hours developed from Grade 1 at baseline
- Grade 3 lymphocyte count decreased

If any of the above toxicities is observed during the DLT evaluation period, whether the toxicity is regarded as DLT will be determined based on consultation between the Investigator and Sponsor.

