## 4.1.3. Inclusion Criteria for Dose Expansion Part

- 1. Has a pathologically documented advanced/unresectable or metastatic breast cancer.
- 2. Has documented HER3-positive (HER3-high or HER3-low) disease assessed by IHC assay by the central laboratory from archival tumor tissue or a screening tumor fresh biopsy sample.
- 3. Is able to submit a fresh tumor biopsy sample prior to starting study treatment. (If subjects have already submitted fresh tumor biopsy sample for HER3 expression, resubmission is not necessary.)
- 4. Has documented HER2-negative expression according to American Society of Clinical Oncology College of American Pathologists (ASCO-CAP) guidelines.
- 5. Has documented HR (estrogen and/or progesterone receptor) positive disease with exception of the TNBC cohort (see inclusion criterion #17 below).
- 6. Is refractory to or intolerant to standard treatment, or for whom standard treatment is no longer available.
- 7. With the exception of the TNBC cohort (see inclusion criterion #18 below), has received ≥2 and ≤6 prior chemotherapeutic regimens for breast cancer, ≥2 of which were administered for treatment of advanced/unresectable or metastatic disease. At least 1 prior chemotherapeutic regimen must have included a taxane (eg, paclitaxel, docetaxel), administered in the neoadjuvant, adjuvant, or advanced setting.
- 8. Male or female subjects aged  $\geq$ 20 years in Japan,  $\geq$ 18 years in the US.
- 9. Has an ECOG PS 0-1, with no deterioration over the previous 2 weeks.
- 10. Has LVEF ≥50% by either ECHO or MUGA within 28 days prior to enrollment.
- 11. Has adequate bone marrow reserve and organ function within 7 days prior to enrollment, defined according to the following:

Item	Laboratory value
Platelet count	≥100 000/mm 
Hemoglobin (Hb)	≥9.0 g/dL
Prothrombin time (PT) or PT- international normalized ratio (INR) and partial thromboplastin time (PTT)	≤1.5 × ULN, except for subjects on coumarin-derivative anticoagulants or other similar anticoagulant therapy, who must have PT-INR within therapeutic range as deemed appropriate by the Investigator.
Absolute neutrophil count (ANC)	≥1500/mm³
Creatinine	≤1.5 × ULN, or creatinine clearance ≥50 mL/min as calculated using the Cockcroft-Gault equation
AST/ALT	$\leq$ 3 × ULN (if liver metastases are present, $\leq$ 5 × ULN)
Total bilirubin	≤1.5 × ULN (<3 × ULN in the presence of documented Gilbert's Syndrome [unconjugated hyperbilirubinemia] or liver metastases)

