	Worst Toxicity NCI- CTCAE Version 5.0 Grade (unless otherwise specified)	Schedule Modification for U3-1402		
Pulmonary toxicity	Grade 3 or 4	Permanently discontinue subject from study treatment.		
1 dimonary toxicity	Grade 5 of 1	Toxicity Management:		
		Hospitalization is required.		
		Promptly initiate empiric high-dose methylprednisolone IV treatment (eg, 500-1000 mg/day for 3 days), followed by at least 1.0 mg/kg/day of prednisone (or equivalent) for a minimum of 14 days or until complete resolution of clinical symptoms and chest CT findings, followed by gradual taper over at least 4 weeks.		
		Reimage as clinically indicated.		
		If still no improvement within 3 to 5 days,		
		
 
Reconsider additional work-up for alternative etiologies as described above.
 
		
		
 
Consider other immuno-suppressants and/or treat per local practice.
 
		
Endocrine disorders				
Endocrine	Grade 3	Delay dose until resolved to ≤Grade 2, then:		
disorders		If resolved in ≤14 days, resume U3-1402.		
		If resolved in >14 days, U3-1402 may be resumed after discussion and agreement between the Investigator and Sponsor.		
	Grade 4	Discontinue subject from U3-1402.		
Eye disorders				
Ocular	Grade 3	Delay dose until resolved to ≤Grade 2, then: If resolved in ≤7 days, resume U3-1402.		
		If resolved in >7 days, then reduce U3-1402 by 1 dose level.		
		Ophthalmologist consultation as clinically indicated.		
	Grade 4	Discontinue subject from U3-1402. Ophthalmologist consult as necessary.		
Renal and urinary d	isorders			
Creatinine increased	Grade 3 (>3.0 × baseline; >3.0 - 6.0 × ULN)	Delay dose until resolved to ≤Grade 1 or baseline, then reduce U3-1402 by 1 dose level.		
	Grade 4 (>6.0 × ULN)	Discontinue subject from U3-1402.		

Table 5.2: Dose Delay Criteria and Dose Reduction for U3-1402 (Continued)

	Worst Toxicity NCI- CTCAE Version 5.0 Grade (unless otherwise specified)  Schedule Modification for U3-1402		
Hepatobiliary disord	lers		
AST or ALT increased without TBL increased	Grade 2 (>3.0 - 5.0 × ULN if baseline was normal; >3.0 - 5.0 × baseline if baseline was abnormal)	Continue U3-1402. In subjects without liver metastasis, monitor AST/ALT 24 to 72 hours later, and continue regular monitoring until resolution.	
	if baseline was normal; >5.0 - 20.0 × baseline if	Delay U3-1402 dose until resolved to ≤Grade 1, then: If resolved in ≤7 days, resume U3-1402. If resolved in >7 days, then reduce U3-1402 by 1 dose level.	

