	>8.0-20.0 × ULN if baseline was normal; >8.0-20.0 × baseline level if baseline level was abnormal In subjects with liver metastases, if the baseline level was > 3 × ULN.	Delay U3-1402 dose until resolved to ≤baseline level, then:  If resolved in ≤7 days, resume U3-1402;  If resolved in >7 days, then reduce U3-1402 by 1 dose level.	
	Grade 4 (>20.0 × ULN if baseline was normal; >20.0 × baseline if baseline was abnormal)	Discontinue subject from U3-1402. Gastroenterologist or hepatologist consult as necessary.	
TBL increased	Grade 2 (>1.5 - 3.0 × ULN if baseline was normal; >1.5 - 3.0 × baseline if baseline was abnormal)	If no documented Gilbert's syndrome or liver metastases at baseline, delay U3-1402 until resolved to ≤Grade 1, then:  If resolved in ≤7 days, resume U3-1402;  If resolved in >7 days, reduce U3-1402 by 1 dose level.  If documented Gilbert's syndrome or liver metastases at baseline, continue U3-1402.	

Table 5.2: Dose Delay Criteria and Dose Reduction for U3-1402 (Continued)

	Worst Toxicity NCI- CTCAE Version 5.0 Grade (unless otherwise specified)	Schedule Modification for U3-1402
TBL increased	Grade 3 (>3.0-10.0 × ULN if baseline level was normal; >3.0-10.0 × baseline level if baseline level was abnormal)	
 
If no documented Gilbert's syndrome or liver metastases at baseline, delay U3-1402 dose until resolved to ≤Grade 1, then:
 
If resolved in ≤7 days, reduce U3-1402 by 1 dose level;
 
If resolved in >7 days, discontinue subject from U3-1402.
 

		If documented Gilbert's syndrome or liver metastases at baseline, delay U3-1402 dose until resolved to ≤Grade 2, then:  • If resolved in ≤7 days, reduce U3-1402 by 1 dose level;
		If resolved in >7 days, discontinue subject from U3-1402.
	Grade 4 (>10.0 × ULN if baseline was normal; >10.0 × baseline if baseline was abnormal)	Discontinue subject from U3-1402.
AST or ALT increased and TBL increased	AST or ALT ≥3 × ULN with simultaneous TBL >2 × ULN	Delay U3-1402 until drug-induced liver injury can be ruled out. The Investigator should consult with a gastroenterologist or hepatologist as needed, and the subject should be treated accordingly.  Monitor AST/ALT and TBL twice weekly until resolution or return to baseline.

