Based on currently available clinical safety data for U3-1402, it is recommended that patients receive premedication with antiemetic agents. Suggested agents include a 5-HT3 blocker in combination with another antiemetic or corticosteroid approximately 30 minutes prior to U3-1402 infusion. Choice of agents is based on Investigator's discretion as per local/institutional guidelines. Investigators must also consider providing patients with an antiemetic regimen for subsequent use as needed.

Table 5.2: Dose Delay Criteria and Dose Reduction for U3-1402 (Continued)

	Worst Toxicity NCI- CTCAE Version 5.0 Grade (unless otherwise specified)	Schedule Modification for U3-1402		
Diarrhea/ Colitis	Grade 3	Delay U3-1402 until resolved ≤Grade 1, and consider treatment per local practice/guidelines, then:  If resolved to ≤Grade 1 in ≤7 days, resume U3-1402.  If resolved to ≤Grade 1 in >7 days, then reduce U3-1402 by 1 dose level		
	Grade 4 (Life-threatening consequences; urgent intervention indicated)	Discontinue subject from U3-1402.		
Mucositis oral	Grade 3	Delay U3-1402 until resolved ≤Grade 1, and consider treatment per local practice/guidelines, then:		
		If resolved to ≤Grade 1 in ≤14 days, resume U3-1402; If resolved to ≤Grade 1 in >14 days, then reduce U3-1402 by 1 dose level.		
	Grade 4 (Life-threatening consequences; urgent intervention indicated)	Discontinue subject from U3-1402.		
Other Adverse Events (Nonlaboratory or Laboratory)	Grade 3	Delay U3-1402 until resolved ≤Grade 1 or baseline level, then:  If resolved in ≤7 days, resume U3-1402;  If resolved >7 days, then reduce U3-1402 by 1 dose level.		
	Grade 4 (Life-threatening consequences; urgent intervention indicated)	Discontinue subject from U3-1402.		

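### Table 5.2 can be read as saying continue at TBL >1.5 to 2 × ULN despite Grade 3 or 4 AST/ALT, in subjects with liver metastases or Gilbert's syndrome

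*Combined protocol and SAP*

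**What the plan says.** Four parts of the hepatobiliary block of Table 5.2 bear on this.

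- **TBL increased, Grade 2.** The band is >1.5 to 3.0 × ULN with a normal baseline, or "1.5 - 3.0 × baseline if baseline was abnormal". Subjects with neither condition have the dose delayed. For the others the row reads "If documented Gilbert's syndrome or liver metastases at baseline, continue U3-1402".
- **AST/ALT rows.** Under the heading "AST or ALT increased without TBL increased", Grade 3 leads to a delay. Grade 4 leads to "Discontinue subject from U3-1402. Gastroenterologist or hepatologist consult as necessary".
- **Combined row.** It is triggered by "AST or ALT ≥3 × ULN with simultaneous TBL >2 × ULN". Dosing is held until drug-induced liver injury is ruled out and stops permanently if it cannot be.
- **Hepatitis row.** It orders a delay, but only with known hepatitis B or C at baseline.

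At the end of the table, the row "Other Adverse Events (Nonlaboratory or Laboratory)" orders a delay at Grade 3 and discontinuation at Grade 4. Section 5.4 allows interruption for other events at the investigator's discretion. Section 5.8 lists any significant adverse event, as judged by the investigator, as a reason to take the subject off. No sentence in Section 5.4 or Table 5.2 says which row governs when several match.

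Section 3.1.7 lists "AST or ALT >5 × ULN, if accompanied by blood bilirubin >1.5 × ULN" among the hepatic DLTs. Neighbouring bullets distinguish subjects with liver metastases; this one does not.

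**The concern.** A bilirubin rise together with a large transaminase rise is a worse liver signal than either alone, so the dosing rule should not become more permissive when the second signal appears. In one band of bilirubin, a literal reading of Table 5.2 does exactly that. The exception exempts bilirubin changes in subjects with liver metastases or Gilbert's syndrome, but it is not confined to isolated bilirubin elevation.

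What is at stake is the safety of individual subjects, not an estimate or an error rate. Subjects with liver metastases are expressly admitted, with AST/ALT up to 5 × ULN, and the number of treatment cycles is unlimited. The 24-hour potential Hy's Law reporting rule in Section 8.5 also starts above TBL 2 × ULN, so it does not catch the band either.

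**Working it through.** No figure in the plan needs reproducing. The check is where the rows meet.

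**Inputs.** TBL Grade 2 runs from 1.5R to 3.0R, where R is the ULN if baseline TBL is normal and the baseline value b (in × ULN) otherwise. The combined row needs TBL >2 × ULN and AST/ALT ≥3 × ULN. With a normal AST/ALT baseline, Grade 3 is >5 to 20 × ULN and Grade 4 is >20 × ULN. The Grade 3 cell is incomplete in the public text; its range is inferred from the surviving part and the adjacent grades.

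**Step 1: the band below the combined row.** It runs from 1.5R to 2.0 × ULN.

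- Normal baseline: 1.5 × 1.0 = 1.5, so >1.5 to 2.0, width 0.5 × ULN.
- b = 1.2: 1.5 × 1.2 = 1.8, so >1.8 to 2.0, width 0.2 × ULN.
- The band closes when 1.5b = 2.0, that is b = 2.0/1.5 = 1.33.
- b = 1.5 (the entry limit in Dose Escalation and Dose Finding): Grade 2 starts at 1.5 × 1.5 = 2.25, so there is no band.

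Dose Expansion admits TBL "<3 × ULN in the presence of documented Gilbert's Syndrome [unconjugated hyperbilirubinemia] or liver metastases". Subjects entering with baselines from about 1.33 × ULN upward are outside the band.

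**Step 2: which rows apply.** Liver metastases or Gilbert's syndrome, normal baselines, no known hepatitis B or C, event drug-related. The heading's undefined term is read two ways.

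| TBL (× ULN) | AST (× ULN) | Hepatic rows if increased means >1.5 | Hepatic rows if increased means >2 | Catch-all, if it applies |
|---|---|---|---|---|
| normal | 25 | discontinue | discontinue | not needed |
| 1.8 | 10 | continue | continue; delay | delay |
| 1.8 | 25 | continue | continue; discontinue | discontinue |
| 2.5 | 10 or 25 | continue; combined-row delay | continue; combined-row delay | not needed |

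On the first reading, AST 25 × ULN means discontinue with normal bilirubin but continue with TBL 1.8 × ULN. On the second, two hepatic rows give opposite instructions.

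**Step 3: the protocol's own benchmark.** AST 10 exceeds 5 and TBL 1.8 exceeds 1.5, so the pair meets the Section 3.1.7 DLT bullet.

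**Step 4: abnormal AST/ALT baselines.** Take baseline AST 2 × ULN, now 5.5 × ULN, with TBL 1.8 × ULN. Then 5.5/2 = 2.75 × baseline, below the Grade 2 threshold of 3. A Grade 3 delay starts only above 5 × 2 = 10 × ULN. The rows give continue whichever way the heading is read, although the values pass the DLT cut-off.

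**The case against.** The best defence is that a protective instruction exists on either reading. The two AST/ALT headings look like complements. The combined row sets its bilirubin limit at 2 × ULN, so the other heading should cover everything up to 2 × ULN, and the delay or discontinue row then applies at TBL 1.8. A continue given for one toxicity does not ordinarily cancel a hold required for another: nobody would let the AST/ALT Grade 2 continue cancel a delay for Grade 4 neutropenia. If the heading instead excludes TBL above 1.5 × ULN, the AST/ALT event has no named row and falls to the catch-all, which also delays or stops dosing. Sections 5.4 and 5.8 add discretion.

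Much of this stands, and it lowers the risk. It does not remove the defect. The complement reading is an inference, and the TBL row itself starts at 1.5 × ULN. AST/ALT and bilirubin both have named rows, so a site may not regard the event as an other one. The catch-all's Grade 4 line describes life-threatening consequences, which an asymptomatic AST of 25 × ULN may not match. Discretion is permissive. None of these expressly displaces an explicit continue.

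Two limits also stand. Section 3.1.7 serves MTD estimation in Cycle 1 of Dose Escalation, with DLT status settled between investigator and sponsor; it is a benchmark, not a dosing rule. Incidence is unknown. At the August 2018 cut-off, AST increase was reported in 23 of 56 subjects (41.1%) and ALT increase in 22 (39.3%), all grades. Bilirubin increase was not among the events above 20%, and no AST/ALT or bilirubin event was among the listed SAEs.

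**Conclusion.** The gap is real, narrow and worth correcting. It applies to subjects with liver metastases or Gilbert's syndrome, baseline TBL below about 1.33 × ULN, drug-related Grade 3 or 4 AST/ALT, and Grade 2 TBL no higher than 2 × ULN. There the hepatic rows give continue alone, or continue against delay or discontinue. These are band limits, not patient counts.

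A reader might infer more, and the documents do not support it:

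- *The protocol obliges sites to keep dosing through DLT-level liver injury.* It does not: the catch-all row arguably requires a hold or stop, and the investigator may interrupt in any case.
- *The whole Grade 2 band, up to 3 × ULN or higher with a raised baseline, is unprotected.* Above 2 × ULN with AST/ALT ≥3 × ULN, the more specific combined row is the natural reading. That overlap needs only a minor clarification.
- *Subjects have been harmed.* Nothing reported shows this.

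The conclusion rests on the inferred range of the Grade 3 AST/ALT cell. Any metastasis qualifier in its missing part should be checked against the full protocol. The two-reading table assumes normal AST/ALT baselines and no known hepatitis B or C. With known hepatitis, that row's delay conflicts with the continue instead.

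**What to change.** Amend the hepatobiliary block of Table 5.2 as follows.

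1. Remove the bilirubin restriction from the AST/ALT heading, so that the Grade 3 delay and Grade 4 discontinuation apply at any TBL.
2. Limit the TBL Grade 2 continue to cases where no AST/ALT, combined or hepatitis row requires a delay or discontinuation.
3. State that when several hepatic rows match, any discontinuation governs; otherwise all their conditions for resuming must be met, including the combined-row work-up for drug-induced liver injury. A strictest-action rule would not do, because it does not order two delays with different resumption terms.

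In the Step 2 cases this gives delay at AST 10 and discontinue at AST 25 with TBL 1.8. With TBL 2.5 it gives delay under both sets of conditions at AST 10 and discontinue at AST 25. The Section 3.1.7 cut-off stays as it is.

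The cost is an amendment to wording, with no added patients, visits or tests. There may be a few more holds or discontinuations. In any subject, drug-related Grade 4 AST/ALT with TBL >2 × ULN would now mean discontinuation instead of the combined-row delay, as it already does with normal TBL. The change does not settle abnormal AST/ALT baselines: because those rows count multiples of baseline, some combinations past the DLT cut-off, such as the Step 4 case, would still be continue.

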# 5.5. Method of Assessing Treatment Compliance

All drugs used for the study treatment will be administered by the Investigator or other designated study personnel. Therefore, treatment compliance will be guaranteed as long as the subject attends each visit for the administration of study treatment.

# **5.6.** Prior and Concomitant Medications

#### **5.6.1.** Prior Medications

All prior anticancer treatments or procedures for breast cancer (eg, surgery, radiation therapy, TKI therapy, chemotherapy, and immune checkpoint inhibitor therapy) will be recorded.

#### **5.6.2.** Concomitant Medications

Medications used from Day 1 of Cycle 1 to the follow-up (F/U) visit or 28 days after the last dose of U3-1402 (if the F/U visit is not performed), will be recorded. If the subject begins another anticancer therapy, medications used after these anticancer therapies will not be record. All concomitant medications will be recorded on the eCRF.

Prophylactic treatment for expected toxicities may be administered per Investigator discretion and institution guidelines.

Hematopoietic growth factors may be used per clinical judgment of the Investigator and according to prescribing information and institutional guidelines.

Bisphosphonates (eg, pamidronate or zoledronate) or denosumab for control of bone pain, treatment of bony metastases, or treatment of osteoporosis, may be used per clinical judgment of the Investigator and according to prescribing information and institutional guidelines.

Supportive treatment including management of study drug-related adverse events will be per Investigator discretion.

Subjects taking warfarin should be monitored regularly for changes in prothrombin time or INR.

#### **5.6.3.** Prohibited Concomitant Medications/Activities

The following medications and products will be prohibited from Day 1 of Cycle 1 until end of treatment (EOT):

- Other anticancer therapy, including cytotoxic agents, targeted agents, immunotherapy or endocrine therapy.
- Radiotherapy, except for palliative radiation to known metastatic sites (as long as it does not affect assessment of tumor response). Whenever possible, subject should have a tumor assessment of the lesion(s) prior to receiving radiotherapy in order to rule out progression of disease. In case of Progressive Disease (PD), subjects should be discontinued from the U3-1402 J101 protocol.
- Hormonal replacement therapy.
- Concomitant medications that prolong the QTc interval including but not limited to: antipsychotics, tricyclic/tetracyclic antidepressants, selective serotonin and norepinephrine reuptake inhibitors (SSNRIs), macrolide antibiotics, fluoroquinolone antibacterials, azole antifungals, antimalarials, and antiprotozoals.
  - If the concomitant medication(s) that prolong the QTc interval is unavoidable,
     consider delaying U3-1402 treatment until such drug has cleared from circulation
     (approximately 3 elimination half-lives of the inhibitors) when possible. If the

drug which prolongs the QTc interval is co-administered and U3-1402 treatment cannot be delayed, patients should be closely monitored for adverse reactions.

- Other investigational agents.
- Chloroquine and hydroxychloroquine
- CYP3A4 strong inhibitors including but not limited to: boceprevir, clarithromycin, itraconazole, ketoconazole, lopinavir/ritonavir, nefazodone, telaprevir, telithromycin, voriconazole.
  - If concomitant use of strong CYP3A4 inhibitors is unavoidable, consider delaying U3-1402 treatment until the strong CYP3A4 inhibitors have cleared from circulation (approximately 3 elimination half-lives of the inhibitors) when possible. If a strong CYP3A4 inhibitor is co-administered and U3-1402 treatment cannot be delayed, patients should be closely monitored for adverse reactions.
- [Dose Escalation and Dose Finding Parts Only] Avoid CYP3A4 strong inducers (eg, carbamazepine, phenytoin, and rifampin).
- Organic anion transporting polypeptide (OATP)1B inhibitors including but not limited to: atazanavir, clarithromycin, cyclosporine, erythromycin, gemfibrozil, lopinavir, rifampin, ritonavir, simeprevir. Consult with your local resources as needed to evaluate potential OATP1B inhibitors.
  - If concomitant use of OATP1B inhibitors is unavoidable, consider delaying U3-1402 treatment until the OATP1B inhibitors have cleared from circulation (approximately 3 elimination half-lives of the inhibitors) when possible. If an OATP1B inhibitor is co-administered and U3-1402 treatment cannot be delayed, patients should be closely monitored for adverse reactions.

